7.5. DESCRIPTION OF SUBGROUPS TO BE ANALYZED

Any planned subgroup analyses will be described in the SAP(s).

7.6. STATISTICAL ANALYSIS METHODOLOGY

Continuous variables will be summarized using the mean, standard deviation, median, minimum, and maximum. Categorical variables will be summarized using frequency counts and percentages. Data will be listed in data listings.

Details of the statistical analyses, methods, and data conventions are described in the SAP(s). All statistical tests will be 2-sided and performed using a 0.05 significance level.

Details of multiplicity adjustment, if any, will be fully described in the SAP(s).

7.6.1. Hypothesis Testing on Key Study Endpoints

Hypothesis testing on key study endpoints will be conducted using the FAS.

A sequential testing procedure will be used to control for Type I Error to test the following key study endpoints:

- DUX4 change from baseline (Week 16 or Week 36)
- LMV change from baseline (Week 48)

- FSHD TUG (Week 48)

The testing hierarchy will be provided in the SAP. Each endpoint will be tested at approximately 5% alpha in a hierarchical manner, using the final test-alpha obtained from O'Brien-Fleming Spending Function (Section 7.6.8).

7.6.2. Analysis of Primary Endpoints

The primary endpoint of the placebo-controlled treatment period is the change from baseline in DUX4 activity in affected skeletal muscle at Week 16 or Week 36, as measured by QRT-PCR in a panel of DUX4-regulated gene transcripts. An analysis of covariance (ANCOVA) model will be used to analyze the change from baseline in DUX4 activity in affected skeletal muscle, with repeat number category and treatment group as fixed effects and baseline DUX4 activity in affected skeletal muscle as a covariate. Least-square (LS) mean, standard error, and 95% CI of the LS mean will be provided for each treatment group. The difference in LS means between treatment groups and the 95% CI of the difference will also be calculated. The final p-value will be compared against the significance level of approximately 0.05 (Section 7.6.8). All available data will be used. Details will be provided in the SAP(s).

The FAS will be used for the primary analysis for the placebo-controlled treatment period.

The analysis for the primary endpoint for the OLE is described in Section 7.6.6.

7.6.3. Analysis of Secondary Endpoints

Secondary endpoints (detailed in Section 7.1.2 and Section 7.2.2) will be summarized using descriptive statistics.

Continuous endpoints with multiple post-baseline assessments will be analyzed using mixed-effect model for repeated measures (MMRM) methods including repeat number category, treatment group, visit, and treatment-by-visit interaction as fixed effects and baseline value as a covariate. Continuous endpoints with a single post-baseline assessment will be analyzed using ANCOVA methods, with repeat number category and treatment group as fixed effects and baseline value as a covariate. Secondary endpoints in the OLE will be summarized according to the treatment assigned at randomization. For all subjects, changes in measurements will be calculated relative to measurements obtained at baseline (ie, prior to first dose in the placebo-controlled treatment period).

Further details of these endpoints are presented in Section 7.6.5, Section 7.6.6, and the SAP(s).

7.6.4. Analyses of Exploratory Endpoints

Exploratory endpoints (detailed in Section 7.1.3) will be summarized using descriptive statistics. Confidence intervals will be included as appropriate. When appropriate, continuous exploratory endpoints will also be analyzed using ANCOVA or MMRM methods similar to those used for the primary and secondary endpoints. Any treatment group comparisons will be in the nature of hypothesis generation, and any statistical inference will not have any confirmatory value.

Exploratory endpoints in the OLE will be summarized according to the treatment assigned at randomization.

7.6.5. Pharmacokinetic and Pharmacodynamic Analyses

Plasma PK concentrations at each time point for losmapimod will be presented in listings and summarized in tables. Losmapimod concentrations in skeletal muscle biopsy at each time point will also be presented in listings and summarized in tables. The summary tables will display the following descriptive statistics: n, mean, standard deviation, coefficient of variation, median, minimum, and maximum.

The individual and mean plasma concentrations and the individual and mean concentrations in skeletal muscle biopsies will be presented by collection time in figures on linear scales.

The target engagement estimates of losmapimod in peripheral blood and skeletal muscle biopsies will be presented in listings and summarized in tables. The summary tables will display the following descriptive statistics: n, mean, standard deviation, coefficient of variation, median, minimum, and maximum. Within-group LS means, the associated standard errors and 2-sided 95% CIs, treatment differences in LS means and the associated 2-sided 95% CIs, and 2-sided p-values will be derived from the ANCOVA model and presented in the tables.

Population PK and PK/PD models may be developed to address program objectives that require an integrative interpretation of these study results. These may include investigations of the nature of the PK/PD relationship and the use of these study results as part of a larger model-based data analysis. If population PK and PK/PD analyses are performed, those results will be reported separately from the results of this study.

7.6.6. Safety Analyses

Safety data in the placebo-controlled treatment period will be analyzed using the safety analysis set and summarized by treatment group and visit (if applicable) using descriptive statistics. Safety data in the OLE will be analyzed using the open-label analysis set.

Treatment-emergent AEs will be summarized by MedDRA system organ class and preferred term; separate summaries will be produced for treatment-related AEs, AESIs, SAEs, and discontinuations due to AEs. Laboratory tests, vital signs, findings from physical examinations, and ECGs will be summarized for changes over time during treatment using descriptive statistics.

7.6.7. Other Analyses

Descriptive summaries of demographic and baseline characteristics will be presented by treatment group and overall for the placebo-controlled treatment period and by treatment assigned at randomization and entry point in the OLE.

Efficacy data will be summarized at each scheduled visit in the OLE, and subjects will be grouped according to initial treatment assigned at randomization and entry point of OLE.

Descriptive statistics will include the number of non-missing observations, mean, standard deviation, median, minimum, and maximum for quantitative data. For qualitative data, frequency counts and percentage will be determined. A full description of demographic variables will be included in the SAP(s).

Individual subject demographics and baseline information will be provided in data listings.

Medical history will be coded using MedDRA at the time of each database lock and will be summarized using the number of observations and percentages of subjects reporting each category and listed for each subject.

A list of protocol deviations (major or minor) will be finalized prior to each database lock.

7.6.8. Interim Analyses

One IA will be performed when a minimum of 22 paired muscle biopsies are completed. A group sequential method (O'Brien-Fleming Spending Function) will be used to ensure an overall significance level of 0.05 (double-sided) due to multiple looks at the DUX4 primary endpoint, if the IA is deemed necessary by the Sponsor.

- With a sample size of approximately 22 subjects at IA, the test alpha at IA is approximately 0.001, and the final test alpha is 0.05. If the p-value from the test is <0.001 , then the study may be stopped for efficacy, or continue as planned as decided by the Sponsor. Cumulative exit probability under the alternative hypothesis is approximately 2.3% and approximately 82.3% at the IA and final analysis, respectively (SAS Version 9.4; nQuery 8 – Power and Sample Size for Group Sequential Trials, Version 8.5.1.0).
- With a sample size of 32 subjects at IA, the test alpha at IA is approximately 0.004, and the final test alpha is 0.048. If the p-value from the test is <0.004 , then the trial may be stopped for efficacy, or continue as planned as decided by Sponsor. Cumulative exit probability under the alternative hypothesis is approximately 13.9% and approximately 82.2% at the IA and final analysis, respectively (SAS Version 9.4; nQuery 8 – Power and Sample Size for Group Sequential Trials, Version 8.5.1.0).

The alphas at the time of the IA for sample sizes ranging from 22 to 32 are provided in Table 1.

Table 1: Alpha At Interim Analysis and Final Analysis for Different Sample Sizes At Interim Analysis (O'Brien-Fleming Method)

Interim Analysis Sample Size	Alpha at Interim Analysis	Alpha at Final
22	0.000567	0.049755
23	0.000736	0.049685
24	0.000951	0.049596
25	0.001203	0.049493
26	0.001474	0.049384
27	0.001803	0.049253

Interim Analysis Sample Size	Alpha at Interim Analysis	Alpha at Final
28	0.002173	0.049107
29	0.002556	0.048959
30	0.003005	0.048787
31	0.003496	0.048602
32	0.004027	0.048405

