Secondary endpoints will be summarized using descriptive statistics. Continuous endpoints with multiple post-baseline assessments will be analyzed using mixed-effect model for repeated measures methods including repeat number category, treatment group, visit, and treatment-by-visit interaction as fixed effects and baseline value as a covariate; continuous endpoints with a single post-baseline assessment will be analyzed using ANCOVA methods, with repeat number category and treatment group as fixed effects and baseline value as a covariate.

Secondary endpoints in the OLE will be summarized according to the treatment assigned at randomization. For all subjects, changes in measurements will be calculated relative to measurements obtained at baseline (ie, prior to first dose in the placebo-controlled treatment period).

Hypothesis testing on key study endpoints will be conducted using the FAS. A sequential testing procedure will be used to control for Type I Error to test the following key study endpoints: DUX4 change from baseline at Week 16 or Week 36; LMV change from baseline at Week 48, and FSHD TUG change from baseline at Week 48.

Safety data in the placebo-controlled treatment period will be analyzed using the safety analysis set and summarized by treatment group and visit (if applicable) using descriptive statistics. Safety data in the OLE will be analyzed using the open-label analysis set. Treatment-emergent AEs will be summarized by Medical Dictionary for Regulatory Activities system organ class and preferred term; separate summaries will be produced for treatment-related AEs, AESIs, SAEs, and discontinuations due to AEs. Laboratory tests, vital signs, findings from physical examinations, and ECGs will be summarized for changes over time during treatment using descriptive statistics.

Interim Analysis

One interim analysis (IA) will be performed after a minimum of 22 paired muscle biopsies have been collected. A group sequential method (O'Brien Fleming Spending Function) will be used to ensure an overall significance level of 0.05 (double- sided) due to multiple looks at the DUX4 primary endpoint.

Version and Date of Protocol: Version 5.0, 16 August 2022

LIST OF ABBREVIATIONS

Abbreviation	Definition
3D	3-dimensional
β -hCG	β -human chorionic gonadotropin
AE	adverse event
AESI	adverse event of special interest
ANCOVA	analysis of covariance
AUC	area under the plasma concentration-time curve

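### Protocol 7.6.8 names an O'Brien-Fleming spending function but tabulates the classical O'Brien-Fleming boundary, and the 13.9% chance of early exit at 32 subjects does not follow from the alphas beside it

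*Protocol*

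**What the plan says.** Protocol 7.6.8 states the method: "A group sequential method (O'Brien-Fleming Spending Function) will be used to ensure an overall significance level of 0.05 (double-sided"). The synopsis uses the same name ("A group sequential method (O'Brien Fleming Spending Function) will be used"). Section 7.6.1 carries it into the hierarchy of DUX4, LMV and FSHD TUG, each tested "using the final test-alpha obtained from O'Brien-Fleming Spending Function (Section 7.6.8").

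Section 7.6.8 then works two cases.

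- About 22 subjects: "the test alpha at IA is approximately 0.001, and the final test alpha is 0.05". "Cumulative exit probability under the alternative hypothesis is approximately 2.3% and approximately 82.3% at the IA and final analysis, respectively".
- 32 subjects: "With a sample size of 32 subjects at IA, the test alpha at IA is approximately 0.004, and the final test alpha is 0.048". "Cumulative exit probability under the alternative hypothesis is approximately 13.9% and approximately 82.2% at the IA and final analysis, respectively".

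It adds that "The alphas at the time of the IA for sample sizes ranging from 22 to 32 are provided in Table 1". The heading of Table 1 speaks of the O'Brien-Fleming method and does not mention spending. Its first row is 0.000567/0.049755 (n=22) and its last is 0.004027/0.048405 (n=32).

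**The concern.** The classical O'Brien-Fleming boundary and an O'Brien-Fleming-type spending function are related but give different thresholds. At n=32 the interim alpha is 0.0040 under the first. Under the second it is 0.0022 or 0.0043, depending on whether 0.025 is spent on each side or 0.05 in total. A statistician who implemented the method the protocol names would therefore not obtain the thresholds it prints.

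The exit probability is the design's statement of how likely an early efficacy crossing is if the assumed effect is true. If it was computed from a boundary other than the printed one, the sponsor has a wrong figure for that property. The final alpha also matters beyond DUX4, because 7.6.1 uses it for every step of the hierarchy.

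**Working it through.** **Inputs.** Effect size 0.70, N=68 evaluable, 1:1 allocation, two-sided 0.05 (Protocol 7.3); two looks, interim n from 22 to 32 (7.6.8). Information fraction t = n/68. The drift of the final test statistic is 0.70 × √(68/4) = 2.886, and the correlation between looks is √t. Fixed-design power at N=68 is 82.3% on normal theory and 81.2% for a t-test, so the protocol's cumulative 82.2–82.3% is on the normal-theory scale.

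**Step 1: reproduce Table 1.** The classical O'Brien-Fleming boundary has interim critical value C/√t and final critical value C, with C chosen so that overall two-sided alpha is 0.05. With t rounded to three decimals, all 11 rows reproduce to six decimals. The end rows are:

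- n=22, t=0.324: C=1.9621, interim 1.9621/√0.324 = 3.447; alphas 0.000567/0.049755.
- n=32, t=0.471: C=1.9738, interim 1.9738/√0.471 = 2.876; alphas 0.004027/0.048405.

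The alphas in the text are these two rows rounded.

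**Step 2: try the named method.** The O'Brien-Fleming-type spending function has two usual forms. Spending 0.025 on each side gives interim alpha 2 × [2 − 2Φ(2.2414/√t)]. Spending a total of 0.05 gives 2 − 2Φ(1.960/√t). The final alpha is solved so that the overall level is 0.05.

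| Boundary | n=22 alphas | n=32 alphas |
|---|---|---|
| Table 1 (classical) | 0.000567/0.049755 | 0.004027/0.048405 |
| Spending, 0.025 per side | 0.000163/0.049943 | 0.002171/0.049280 |
| Spending, total 0.05 | 0.000569/0.049754 | 0.004275/0.048275 |

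Neither spending form gives the n=32 row.

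**Step 3: exit probabilities at n=32.** At t = 32/68 the interim drift is 2.886 × √(32/68) = 1.980. With Table 1's critical value 2.876, the interim exit probability is 1 − Φ(2.876 − 1.980) = 18.5%; the opposite tail is negligible.

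| n=32 | Interim exit | Cumulative |
|---|---|---|
| Stated in 7.6.8 | 13.9% | 82.2% |
| Table 1, normal theory | 18.5% | 82.05% |
| Table 1, t-test | 15.1% | 80.9% |
| Spending, 0.025 per side, normal theory | 13.88% | 82.18% |
| Spending, total 0.05, normal theory | 19.0% | 82.0% |

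Using the rounded 0.004 instead of 0.004027 gives 18.45%, so rounding does not close the gap. Working backwards, an interim exit of 13.9% at 32/68 implies an interim alpha of about 0.0022. Table 1's alphas with a final N of 76 or 80 still give 18.5% at the interim and raise final power to about 86–88%.

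**Step 4: exit probability at n=22.** Table 1 gives 3.6% on normal theory and 2.1% for a t-test; per-side spending gives 1.7%. The stated figure is 2.3%.

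**Step 5: type I error (normal theory).**

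- Table 1 as printed: 0.0500.
- 0.001/0.05 used literally at n=22: 0.0505.
- 0.004/0.048 used literally at n=32: 0.0496.

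**The case against.** The strongest reply is that little depends on this. Exit probability under the alternative is descriptive. Crossing only allows the sponsor to stop, and the interim itself is at the sponsor's discretion. Every alpha printed in 7.6.8 is a Table 1 value or its rounding, so the thresholds can be found despite the label. All of that stands, and it is why the point is minor.

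Second, only one number discriminates. The cumulative 82.2% is close to both boundaries (82.05% and 82.18%), so the evidence for a mixed bullet is the 13.9%. That is correct, but the gap of 18.5 − 13.9 = 4.6 points is too large for rounding. The t-test does not explain the pair either, because it gives 15.1% with 80.9% cumulative.

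Third, the label is only loosely wrong. After rounding, the total-0.05 spending form gives nearly the same alphas as the text, and Table 1 differs from it by about 0.0002 at n=32. This is fair as to consequence. The six-decimal table nevertheless identifies the classical boundary, and the total-0.05 form gives 19.0% at the interim, further from 13.9%.

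Fourth, the per-side explanation fails at n=22, where it gives 1.7% against the stated 2.3%. This stands: no single boundary and basis tried here reproduces both bullets. The source of the 13.9% is inferred from the match at n=32, since the per-side alphas are not printed for that row. The mismatch itself does not depend on that inference.

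Finally, Protocol section 7 and the introduction to 7.6 leave details to the SAPs, and the supplied SAP covers only the open-label extension. The placebo-period SAP may fix the boundary. The protocol text would still be inconsistent.

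**Conclusion.** The concern holds, at minor severity. At n=32 the stated interim exit probability of 13.9% belongs to a different boundary from the adjacent alphas, which give 18.5% on normal theory or 15.1% for a t-test. The method named in three places is not the method tabulated.

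Error control is sound if Table 1 is used as printed, with overall alpha 0.0500 on normal theory. A simulated t-test at both looks gives 0.0499 at n=22 and 0.0505 at n=32, with a simulation standard error of 0.0002. The literal decision rule at n=22 (0.001, then 0.05) exceeds the nominal level by 0.0505 − 0.05 = 0.0005, which is a rounding matter. The mismatch at n=32 is established with high confidence; its origin is not.

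The figures assume two looks, N=68 evaluable, an effect size of 0.70, and information proportional to the number of paired biopsies. The t-test figures stand in for the planned ANCOVA and ignore its covariates, apart from a check with 28 instead of 30 degrees of freedom, which gives 14.9% at n=32.

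**What to change.** First establish whether the interim has been run. Enrolment was complete by 10 April 2020, the controlled period was 48 weeks, and this protocol version is dated 16 August 2022, so by the protocol's own dates the controlled period was over. If the interim took place, record the boundary that was pre-specified and applied, and do not choose one now.

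Then name that boundary in the synopsis, 7.6.1 and 7.6.8.

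- **If Table 1 governs:** call it the classical O'Brien-Fleming boundary, and take the interim and final alphas, unrounded, from the row for the actual interim n. At n=22 the interim threshold then reads 0.000567, not 0.001. Restate the exit probabilities and say on which basis: normal theory (3.6% at n=22 and 18.5% at n=32; cumulative 82.2% and 82.1%) or t-test (about 2.1% and 15%; cumulative about 81%).
- **If the spending function governs:** state its form and replace Table 1 and the text alphas. With 0.025 per side, n=32 becomes 0.00217/0.0493 and the stated 13.9%/82.2% can stay; n=22 becomes 0.000163/0.0499 with an interim exit of 1.7%.

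The cost is wording and a few figures, plus a new Table 1 in the second case. Sample size does not change.

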8. DATA QUALITY ASSURANCE

This study will be conducted according to the International Council for Harmonisation (ICH) E6(R2) risk and quality processes described in the applicable procedural documents. The quality management approach to be implemented in this study will be documented and will comply with the current ICH guidance on quality and risk management.

8.1. DATA MANAGEMENT

As part of the responsibilities assumed by participating in the study, the investigator agrees to maintain adequate case histories for the subjects treated as part of the research under this protocol. The investigator agrees to maintain accurate eCRFs and source documentation as part of the case histories. These source documents may include laboratory reports, ECG strips, etc.

Study site personnel will enter subject data into Medidata RAVE® (the eCRF program). The analysis data sets will be a combination of these data and data from other sources (eg, laboratory data).

Clinical data management will be performed in accordance with applicable █ standards and data cleaning procedures to ensure the integrity of the data, eg, removing errors and inconsistencies in the data. Adverse event terms will be coded using MedDRA, an internal validated medical dictionary, and concomitant medications will be coded using the World Health Organization Drug Dictionary.

After final database lock, each study site will receive a CD-ROM containing all of their site specific eCRF data as entered into the Medidata RAVE system for the study, including full discrepancy and audit history. Additionally, a CD-ROM copy of all of the study site's data from the study will be created and sent to the sponsor for storage. █ will maintain a duplicate CD-ROM copy for their records. In all cases, subject initials will not be collected or transmitted to the sponsor.

9. ETHICS

9.1. INDEPENDENT ETHICS COMMITTEE OR INSTITUTIONAL REVIEW BOARD

Federal regulations and the ICH guidelines require that approval be obtained from an IRB/IEC before participation of human subjects in research studies. Before study onset, the protocol, informed consent, advertisements to be used for the recruitment of study subjects, and any other written information regarding this study to be provided to the subject or the subject's legal guardian must be approved by the IRB/IEC. Documentation of all IRB/IEC approvals and of the IRB/IEC compliance with ICH harmonised tripartite guideline E6(R2): Good Clinical Practice (GCP) will be maintained by the site and will be available for review by the sponsor or its designee.

All IRB/IEC approvals should be signed by the IRB/IEC chairman or designee and must identify the IRB/IEC name and address, the clinical protocol by title or protocol number or both, and the date on which approval or a favorable opinion was granted.

The investigator is responsible for providing written summaries of the progress and status of the study at intervals not exceeding 1 year or otherwise specified by the IRB/IEC. The investigator must promptly supply the sponsor or its designee, the IRB/IEC, and, where applicable, the institution, with written reports on any changes significantly affecting the conduct of the study or increasing the risk to subjects.

